The consent form will be translated into Spanish and submitted the IRB once it is ready. A copy of the English consent form is attached with this IRB package.

C6. Randomization

After a home visit to consent and collect baseline data, patients will be randomized in a 1:1 ratio, to receive either: (1) CAPABLE intervention or (2) usual care. The schedule will be stratified by surgical vs. non-surgical hospital admission due to the marked difference in functional recovery.¹³ Cases will be randomized within variable-sized blocks from 4 to 8 participants. These procedures will maintain allocation concealment throughout the trial, consistent with the CONSORT recommendations.¹⁴ No research staff or investigator interacting with potential participants will be able to anticipate treatment allocation of the next assignment because of variable block sizes.

C7. Patient interviews

Study participants will be asked to participate in one interview at the start of the study, a second interview 20 weeks later and a possible third interview in about 52 weeks post study enrollment. Each interview visit will last about 1 hour. During each visit, a trained research interviewer will ask the participant questions about their daily activities, pain level, medical conditions and other questions about their health (see Table 1 below). At the very end of the study, after all of the interviews are completed, another member of the research team may call and speak to the patient briefly about how the study went. All study participants will receive \$25 after each completed in-home interview.

Table 1. Data Sources

MEASURES (CITATION)	MEASURED WHEN	CONSTRUCTS AND MEASUREMENT ATTRIBUTES	TESTED IN SPANISH SPEAKING POPULATIONS
Demographics	BL, 20, 52 weeks	Age, race, sex, insurance attributes, live with others, reason for hospital stay,	Yes
ADLS – Katz ^{72,73,75} 0-16	BL, 20,52 weeks	Bathing, dressing (upper and lower), toileting, transferring, toileting, feeding, walking across small room. Cronbach's alpha 0.87-0.94. ⁷⁷	Yes
IADL 0-16 ⁷⁶	BL, 20,52 weeks	Ability to use the telephone, shop, prepare food, light housekeeping, wash laundry, take own medication, travel independently, and manage finances	Yes
Prior hx ADLs, IADLs	BL	ADL and IADL assessment prior to hospitalization	Yes
PROMIS Global 10	BL, 20,52 weeks	Overall health, quality of life, social activities, self-care, pain, fatigue, anxiety/depression, and mobility	Yes ⁷⁷

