Home hazards-CDC Home Hazard Index 0-41	BL, 20 weeks	42 items- general household, kitchen, bathroom, bedroom and stairways. No psychometric data available.	Yes
Depression PHQ-9 ^{78,79} 0-27	BL, 20,52 weeks	Identification of Depression. Sensitivity 88%, specificity 78%	Yes ⁸⁰
Pain – Brief Pain Inventory ⁸¹	BL, 20,52 weeks	Severity of pain, impact of pain on daily function, location of pain, pain medications and amount of pain relief in the past week	Yes
Patient Activation ^{82,83}	BL, 20 weeks	General preventive behaviors, disease-specific behaviors, and health fatalism Reliability 0.89, Cronbach alpha 0.87. Test-Retest reliability 93%	Yes ⁸²
Control Strategy Use ^{84,85}	BL, 20 weeks	Behavioral and cognitive processes that facilitate adaptation to life challenges Cronbach alpha = 0.69	Not yet—will do psychometric testing in this study
Charlson Comordity Index ⁸⁶	BL, 20,52 weeks	Co-morbidity, will ascertain from medical record	From medical chart ^{86,87}
Readmission rates	BL, 33 weeks	Purpose-built data collection form to be collected by research team	Yes
Medical utilization and costs	BL, 52 weeks	Purpose-built data collection form to be collected by research team	Yes
Formal and informal care	BL, 20, 52 weeks	Helpers section from National Health and Aging Trends Study ⁸⁸	Yes

C8. Spanish Translation

All data collection materials such as the patient survey, consent form, screener and scripts will be translated into Spanish via a professional translation service. Spanish copies will be submitted to the IRB prior to recruiting Spanish speaking study participants.

D. Data to be employed

D1. Data Sources

Data will be collected from the following sources:

- VNSNY CHOICE Medicare Advantage electronic medical record
- VNSNY electronic health record administrative variables
- OASIS data (start of care, transfers, resumption of care and discharge)

- Telephone screening recruitment calls
- In-home interviews

D2. Data Collection and Management

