proposed mediators, we will use models specifically developed for testing mediation effects in two-wave intervention trials and applied by our team for continuous outcome variables and for event outcomes. We will use structural equation modeling with baseline-adjusted changes in potential mediators regressed on the intervention condition to determine one leg of the mediation effect (a path) and baseline-adjusted changes in primary and secondary outcome variables regressed on changes in the mediator to estimate the second leg of the mediation effect (b path). The remaining adjusted intervention effect on the outcome variable represents the direct or unmediated effect (c' path). Mplus software calculates standard errors for mediation effect (a*b) using the Sobel or delta method and bootstrapping methods are also available to test the significance of the mediated effect. We will interpret and quantify significant mediation pathways to identify important intervention mechanisms. Furthermore, the proportion of the total intervention effect that can be attributed to any particular mediator will be calculated by $(a*b)/((a*b)+c')$. Multiple group structural equation models and associated nested comparisons of constrained and unconstrained models will also be employed to examine if mediation effects differ significantly by the subgroups listed above (secondary aim 4). Collectively, the analyses in secondary aim 4 will identify the pathways by which the intervention is delivering intended effects on outcomes and the patient subgroups that are particularly likely to benefit via specific pathways.

We have elected to not consider interim analyses in this study due to the extended time for recruitment and the low likelihood of a sufficiently large effect that would make it possible to stop early. However, we will revisit this decision with the DSMB at its first organizational meeting.

F. Risks

F1. Risks and Benefits to participants

- i. **Potential Risks:** The study intervention does not pose risks greater in and of themselves than those ordinarily encountered in daily life or during the performance of routine physical or psychological examinations or tests. However, this study involves exercise and discussion of changes of medication regimens with primary care providers. The potential risks to study participants include falls from increased exercise or participant changing own medication regimen after discussion of medications.

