- ii. **Potential Benefits:** Participants in the control group will not directly benefit. Participants in the intervention group will receive study visits from a Nurse, an Occupational Therapist, and a Handyman.

F2. Data Safety and Monitoring Plan

Please see the full DSMP included with this IRB package for additional information on the risks related to this study.

Early stopping rules: All Adverse events will be classified by severity and expectedness. Tracking reports will ensure that any statistically significant increases in death, hospitalization, or falls resulting in hospitalization are identified. Statistical tests of group difference will be conducted to determine if rates of serious adverse events differ between intervention and control groups. The DSMB will decide a threshold for the difference required between groups to consider stopping. Because there will be surveillance bias, as the control group participants will be much less likely to report adverse events on a regular basis, the DSMB may consider a difference in less than 50% increase in adverse events to be an acceptable difference.

G. Data Storage and Confidentiality

Data with identifiers will be used and stored by the research and intervention teams at VNSNY, all subject-identifying information on paper in the office will be kept in locked files accessible only to study staff at VNSNY, or, if in use in the field (assignment sheets to field interviewers and intervention staff), will be kept securely and destroyed at the earliest opportunity. Access to shared-drive network folders will be electronically restricted to the appropriate team members. Dates of birth and initials will be used along with the study IDs to confirm appropriate merging of data from different sources. All study staff have or will be thoroughly trained in the need to maintain strict confidentiality.

Legal Risks such as the risks that would be associated with a breach of confidentiality

In the unlikely event that a breach in confidentiality should occur, the study team will take the appropriate steps to inform the study participant and both VNS and Johns Hopkins University (JHU) IRBs that such an event has occurred.

Financial Risks

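### The supplied protocol and SAP specify no falls measure collected the same way in both arms, so a moderate increase in falls could not be reliably detected or told apart from unequal reporting.

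*Combined protocol and SAP*

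**What the plan says.** **The risk.** Section F1 states: "The potential risks to study participants include falls from increased exercise or participant changing own medication regimen after discussion of medications". The intervention includes balance and strength exercises and medication simplification (section B), so both risks follow from its content.

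**What is tracked.** Section F2 begins with general handling: "All Adverse events will be classified by severity and expectedness". It then names the events to be followed: "Tracking reports will ensure that any statistically significant increases in death, hospitalization, or falls resulting in hospitalization are identified". The planned between-arm test concerns serious events: "Statistical tests of group difference will be conducted to determine if rates of serious adverse events differ between intervention and control groups".

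**What F2 concedes.** It acknowledges surveillance bias because "the control group participants will be much less likely to report adverse events on a regular basis". It leaves the stopping threshold to the DSMB, which may regard an excess of adverse events below 50% as acceptable.

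**What the interviews cover.** Section C7 ties the interview content to Table 1. The table has no entry for number of falls, fall injury or self-initiated medication change at baseline, 20 or 52 weeks. The nearest entry is "Home hazards-CDC Home Hazard Index 0-41", described as "42 items- general household, kitchen, bathroom, bedroom and stairways". That measures the dwelling, not falls.

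**What the SAP covers.** The primary outcome is the Katz score. The discrete secondary outcomes are hospitalization and admission to skilled home health care, skilled nursing facility or nursing home. Falls are not among them.

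**Other sources.** Section D2 identifies admissions from claims in both arms. Section E3, aim 2, obtains inpatient, outpatient and physician claims for both cohorts, for costing. F2 refers to a fuller data safety and monitoring plan that was not supplied.

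**The concern.** A fall that leads to admission can be sought in both arms, because admissions come from claims. Any other fall enters the study only if someone reports it, and the opportunities to report differ. CAPABLE participants have up to 10 sessions with a therapist or nurse. Usual-care participants have no study-clinician visits and, as far as the supplied text shows, only newsletters until the week-20 interview, which has no listed falls question.

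At stake is the safety comparison for a risk the protocol itself names. More reported falls under CAPABLE could mean more falls or more contact. Similar numbers of hospitalized falls would be weak reassurance, because such events are likely to be few in a trial of this size. The same gap would hide a benefit: section C3.3 includes fall-recovery training, grab bars and rails, and the plan has no symmetric measure to show whether falls went down.

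**Working it through.** **1. The plan's own design figure.** Inputs from section E2: two-sided 0.05, 80% power, effects of 0.60, 0.50 and 0.40 SD, 25% attrition. A two-sample t-test needs 45, 64 and 100 analysed per arm. Dividing by 0.75 gives 60, 85.3 and 133.3, against the stated 60, 85 and 134. With 100 per arm and 0.40 SD, power is 0.80. The stated sample size reproduces. The documents give no design figure for falls.

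**2. Sources set side by side.**

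| Type of fall | Source in the supplied text | Same in both arms? |
|---|---|---|
| Leads to hospital admission | Tracking reports (F2); admissions from claims (D2) | Admissions yes; how a fall is identified as the cause is not stated |
| Treated without admission | Adverse event reports (F2); outpatient and physician claims (E3), used for cost | Claims yes, but no falls analysis is planned; reports no |
| Not treated | Adverse event reports (F2) | No, by F2's own statement |

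**3. Power for a 50% increase.** All control risks are assumptions. The sizes are 134 per arm enrolled and 100 per arm after 25% attrition. The normal approximation is

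Power = Φ{[d − 1.96·√(2p̄(1−p̄)/n)] / √[(p₁(1−p₁) + p₂(1−p₂))/n]}, with p₂ = 1.5p₁, d = p₂ − p₁ and p̄ = (p₁ + p₂)/2.

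Example: p₁ = 0.03, p₂ = 0.045, n = 134. The two standard errors are 0.0232 and 0.0232, so Φ[(0.015 − 0.0455)/0.0232] = Φ(−1.31) = 0.094. The expected counts are 134 × 0.03 = 4 and 134 × 0.045 = 6.

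The documents do not name a test for falls, so the table also gives exact power of Fisher's test.

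| Outcome (assumed) | Control risk | n per arm | Fisher | Normal approx. |
|---|---|---|---|---|
| Hospitalized fall | 2% | 134 | 2.7% | 7.5% |
| Hospitalized fall | 3% | 134 | 4.6% | 9.4% |
| Hospitalized fall | 5% | 134 | 8.1% | 13% |
| Any fall | 20% | 134 | 42% | 47% |
| Any fall | 30% | 134 | 68% | 72% |
| Any fall | 20% | 100 | 31% | 37% |
| Any fall | 30% | 100 | 53% | 59% |
| Any fall | 40% | 100 | 79% | 81% |

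By the normal approximation with 134 per arm, the smallest relative risk detectable with 80% power is 5.1, 4.0 and 3.1 for hospitalized falls at 2%, 3% and 5%. For any fall it is 1.76, 1.55 and 1.43 at 20%, 30% and 40%.

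**4. Effect of unequal reporting.** Apparent relative risk = true relative risk × (share reported under CAPABLE ÷ share reported under usual care). The shares are assumptions. With no true effect, 0.90/0.60 gives 1.5 and 0.90/0.45 gives 2.0. The first equals the 50% figure in F2. A true relative risk of 1.5 with equal reporting also shows as 1.5. Adverse event reports alone cannot separate the two situations.

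**The case against.** Several stronger readings are tempting, and the documents do not support them.

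- *That only hospitalized falls are tracked.* F2 classifies all adverse events, so a reported fall without admission can be recorded. The fault is unequal ascertainment, not absence of any record.
- *That an increase could not be detected at all.* A relative risk of about 3 to 5 in hospitalized falls has reasonable power at the assumed risks. The limit applies to moderate increases.
- *That a fall treated in an emergency department or clinic is lost.* Outpatient and physician claims are to be obtained for both arms under E3, aim 2. What is missing is a plan to look for falls in them.
- *That medication self-change goes unrecorded.* The nurse reviews medication management in CAPABLE (C3.3), so a change may surface there. No measure common to both arms is listed.
- *That the trial expects this harm.* F1 calls falls a potential risk and says the intervention poses no risk beyond those of daily life. That falls come first in a two-item sentence carries no weight.

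The file is also incomplete. The full safety monitoring plan and the questionnaire were not supplied, and either might contain a falls question. This stands, and limits the point to the supplied documents. F2's own statement about unequal reporting nevertheless suggests that solicitation was not expected to be symmetric.

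Finally, the power figures rest on assumed risks and vary with the test, and at 100 per arm an interview question still falls short of 80% at assumed risks of 20% to 30%. That too stands. The main gain from the question is a comparison not driven by contact frequency; better power is secondary.

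**Conclusion.** The point holds in limited form. In the supplied protocol and SAP, a named potential risk has no measure collected equally in both arms. Hospitalized falls are the only fall type named for tracking, and other falls rely on reports that the protocol describes as unequal. A moderate increase could not be reliably detected or separated from reporting bias.

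The size can only be illustrated. For a 50% increase in hospitalized falls, power is roughly 3% to 13% across assumed control risks of 2% to 5% and both calculations. A reporting share of 90% against 60%, also assumed, is enough to produce a spurious relative risk of 1.5. The absence of a falls measure does not depend on these assumptions.

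No stated number is wrong, and the primary ADL comparison is unaffected. This is a worthwhile, inexpensive improvement to the safety comparison.

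**What to change.** First check the full safety monitoring plan and the questionnaire for a falls question asked of both arms. If there is none:

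1. Add identically worded questions to the existing masked interviews in both arms, at baseline, week 20 and, where held, week 52: number of falls (since the last interview, or over a fixed look-back period at baseline), any injury or care sought, and any medication changed without the prescriber. Week 20 matters most, because C7 describes the third interview only as possible.
2. Identify fall-coded emergency and outpatient events, in both arms, from the claims already to be obtained under E3, aim 2. D2 mentions facility and procedure codes, so confirm that diagnosis fields are available.
3. In F2, base the between-arm falls comparison on these symmetric sources. List events volunteered at therapist or nurse sessions separately.
4. Label any accompanying power figures as illustrations under assumed fall rates.

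The cost is a few minutes in a one-hour interview and some coding work, with no new visits or staff. Recall over 20 to 32 weeks will be imperfect, and the error may differ by arm because participants know their allocation and CAPABLE participants receive fall-related coaching. Claims do not depend on recall, but CAPABLE contact could itself prompt care-seeking, so the two sources should be read together. None of this sets a stopping threshold, which remains with the DSMB.

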The overall goal of this rigorous experimental study is to test the effectiveness of a multi-component home-based intervention to enhance physical function of patients who have ADL difficulties and have been recently hospitalized compared to a usual care control group. We will use an intention-to-treat (ITT) analysis to compare these two conditions; data from all participants will be analyzed as members of their randomly assigned treatment group. The primary outcome will be the Katz measure of difficulties with activities of daily living (ADLs). Scores on this measure range from 0 to 16, with higher scores indicating greater disability. In addition to the primary outcome, several additional comparisons will be conducted on secondary outcome variables. Because there is only one primary outcome measure, no adjustment for type I error is made for multiple comparisons, and a statistically significant finding will be indicated if the p-value is less than 0.05 for the treatment effect. This would indicate a type I error rate of less than 5% for rejecting the null hypothesis of no difference between treatment groups if the null hypothesis is, in fact, true. Two-tailed tests will be used for all statistical comparisons. P-values will also be reported for the secondary outcome analyses but these p-values from the secondary analyses will be considered descriptive indicators of the intervention impact on those measures and not as absolute indicators for null hypothesis testing.

Comparison Group Selection

This is a two group comparison. A total of 268 participants will be enrolled and randomized in a 1 to 1 ratio to either the intervention condition or to a usual care control group, with 200 participants expected to provide outcome data after accounting for 25% attrition. A total of 200 participants for analysis will provide 80% power to detect a clinically meaningful difference of 0.40 standard deviation units between intervention and usual care groups on the primary outcome measure of ADL difficulty.

Type of Statistical Test

This two group comparison will be a test of **superiority**. A two-tailed test will be used with the type I error rate set at 0.05.

Statistical Test of Hypothesis (Primary Outcome)

The **method** to be used to calculate the p-value given the null hypothesis of no difference between the two treatment groups is an analysis of covariance (ANCOVA). The outcome variable will be the 20-week Katz summary disability score. Treatment group (intervention vs. usual care control) will be the primary independent variable. The baseline (pre-treatment) Katz summary disability score will be the primary covariate. Other baseline demographic (e.g., gender), functional ability, and clinical variables (e.g., Charlson comorbidity index, pre-hospitalization ADL function) may be included as additional covariates if there are any random imbalances on those variables across intervention groups or if they are significantly correlated with the 20-week Katz score after adjustment for the baseline Katz score.

Method of Estimation (Primary Outcome)

An ordinary least squares estimate of the mean difference, adjusted for covariates, will be used. Consistent with the pre-specified type I error rate of 0.05, 95% confidence intervals will be reported for this covariate-adjusted mean difference.

Parameter Dispersion Type (Primary Outcome)

The standard error of the mean will be used to characterize dispersion and to calculate the 95% confidence interval.

Statistical Tests of Hypotheses (Secondary Outcomes)

Secondary outcomes include discrete events such as hospitalization and admission to skilled home health care, skilled nursing facility, and nursing home. Time to event (i.e., survival analysis) models will be used to examine intervention impact on these discrete outcomes. Cox regression (proportional hazards) models will be conducted with intervention group as the primary predictor variable and baseline demographic (e.g., gender), functional ability, and clinical variables (e.g., Charlson comorbidity index, pre-hospitalization ADL function) included as covariates.

Method of Estimation (Secondary Outcomes)

Hazard ratios (with usual care as the reference group) will determine the degree to which the intervention was effective in reducing the rates of (or delaying) these discrete event outcomes. All hazard ratios will be accompanied with 95% confidence intervals to aid interpretation and to characterize potential variability of the true intervention effect.

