The usual care group will not receive additional visits from study clinicians. All participants will be re-evaluated at 20 and 52 weeks. Re-admission to skilled home health care, acute care hospitalization, skilled nursing facility, and nursing home admission will be assessed via VNSNY CHOICE claims data at 90 days (33 weeks) post follow up assessment. We will evaluate overall health care costs at 52 weeks (long-term impact). Outcome measures will be assessed by interviewers and analysts masked to treatment assignment and without interventionist contact. Each design component is described below.

Figure 1: Study Flow

C2. Characteristics of study population

Participants will be community dwelling older adults who agree to participate in the study. We will enroll approx. 268 patients over a 3 year period, enrolling about 100 participants per year. Eligible patients will be VNSNY CHOICE Medicare Advantage Health Plan members who received skilled home health care following an acute hospitalization. We will recruit 60 days after the hospital discharge so that we are capturing residual ADL difficulty after the initial healing and strengthening has occurred. Inclusion criteria include: 1) age 65 or older; 2) 60 days after an acute care hospitalization followed by VNSNY home care episode; 3) Difficulty with at least 1 ADL; 4) Member of the VNSNY CHOICE Medicare Advantage Health Plan; 5) Are able to stand with or without assistance; 6) Are available during the study timeframe. Exclusion criteria includes: 1) Significant cognitive impairment based on the Callahan 6-item cognitive screening tool; 2) Does not speak English or Spanish as their primary language; 3) Is actively receiving cancer treatment; 4) Plans to move in less than 1 year.

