Sample size calculations are based on our ability to detect clinically meaningful effect sizes for CAPABLE on the primary outcome of mean ADL difficulty score. All calculations are based on two-sided tests of 0.05 significance. Assuming a conservative attrition rate of 25% during the 20-week follow-up period, (we have consistently had 13% attrition in prior CAPABLE studies)¹⁰ we would need to enroll 60, 85, and 134 participants per treatment arm to detect, with 80% power, an intervention effect size of 0.60, 0.50, and 0.40, standard deviation units, respectively, at 20 weeks after baseline. Preliminary data showed a 41% reduction in ADL difficulty (*0.76 standard deviation units*) in the post-hospitalized group.¹⁰ Smaller effects of 0.57 to 0.60 standard deviation units were noted for other outcomes, and effect sizes of 0.63 for ADL difficulties and 0.62 for IADL difficulties were obtained in a small RCT pilot.¹⁵ By enrolling at least 268 participants, we anticipate having 20-week outcome data (primary endpoint) on 200 participants after 25% attrition. This sample size will provide excellent power to detect clinically meaningful differences between intervention and usual care groups.

E3. Primary study aims:

- 1. Test the effectiveness of CAPABLE in reducing ADL difficulties compared to usual care after 20 weeks of intervention.** We will address this aim using an analysis of covariance on the 20-week Katz summary disability score with treatment group as the primary independent variable and the baseline Katz score as the primary covariate. Other baseline demographic (e.g., gender) functional ability, and clinical variables (e.g., Charlson comorbidity index, pre-hospitalization ADL function) will be included as covariates if there are any random imbalances on those variables across intervention groups or if they are significantly correlated with the 20-week Katz score after adjustment for the baseline Katz score.

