- 1) Test the effectiveness of CAPABLE for reducing ADL difficulties compared to usual care baseline to 52 weeks.** Additional, multilevel longitudinal analyses will incorporate the 52-week outcome data to examine the maintenance of any intervention effects. In these models, time since randomization (20 vs. 52 weeks) will be examined as a within-person or repeated measures factor, and group*time interaction tests will determine whether there are different trajectories of change in ADL (primary outcome) and the other continuous secondary outcomes (IADL, depressive symptoms).
- 2) Explore whether the intervention has differential effectiveness across subgroups.** We will explore subgroup effects and heterogeneity of intervention response. Key subgroups will include those defined by gender, ethnicity, living arrangement, (e.g., with vs. without a co-residing caregiver), type of hospitalization (e.g., surgical vs. nonsurgical) and medical complexity (e.g., high vs. low Charlson comorbidity scores). We will add interaction terms to the models to test empirically whether the intervention is more or less effective in one group compared to a reference group, and examine stratified analyses where we observe significant interaction effects.
- 3) Examine theoretically-driven mediation pathways to identify potential mechanisms of intervention effectiveness.** We hypothesize multiple intermediate variables as possible mediators of the intervention's impact including changes in depression, pain, and control strategy use. For each of these

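### The primary ANCOVA leaves out the randomisation stratum and picks its extra covariates by a data-driven rule that is worded differently in the protocol and the SAP

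*Combined protocol and SAP*

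**What the plan says.** Protocol C6 (Randomization): "The schedule will be stratified by surgical vs. non-surgical hospital admission due to the marked difference in functional recovery".

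The primary model is stated twice. Both versions fix the 20-week Katz score as outcome, treatment group as the main term and baseline Katz as the primary covariate. They then add further baseline variables, given only as examples (gender, Charlson index, pre-hospitalization ADL function):

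- Protocol E3, aim 1: these "will be included as covariates if there are any random imbalances on those variables across intervention groups", or if they correlate significantly with the 20-week score after adjustment for baseline Katz.
- SAP, Statistical Test of Hypothesis (Primary Outcome): these "may be included as additional covariates if there are any random imbalances on those variables across intervention groups or if they are significantly correlated"; the correlation meant is the same one as in the protocol.

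The SAP's Method of Estimation adds: "An ordinary least squares estimate of the mean difference, adjusted for covariates, will be used". The Statistical Analysis Overview sets the success criterion: "a statistically significant finding will be indicated if the p-value is less than 0.05 for the treatment effect".

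The surgical/non-surgical split is named in neither statement of the primary model. In the analysis text it appears only among the exploratory subgroups of E4, aim 2: "type of hospitalization (e.g., surgical vs. nonsurgical) and medical complexity".

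**The concern.** Two things do not fit together. First, the trial randomises within a factor that it calls strongly prognostic, then writes a primary model that does not mention it. The usual rule is to analyse as randomised; otherwise the standard error does not reflect the balance that stratification provides.

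Second, the remaining covariates depend on the data. The candidate list is open, imbalance has no stated measure or size, and the second trigger needs the 20-week outcome. Under the protocol's *will*, every triggered variable goes in. Under the SAP's *may*, someone decides, so several models are permissible and each has its own p-value. The success criterion presumes that there is one. What is at stake is whether a result close to 0.05 can be defended as the result that was planned.

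**Working it through.** **Inputs from the documents.** 1:1 allocation in variable blocks of 4 to 8, stratified (C6); two-sided 0.05, 80% power, 25% attrition, 134 per arm for 0.40 SD (E2); 200 analysed (SAP, Comparison Group Selection). The documents give no covariate effects, correlations or stratum shares. Those below are assumptions, shown as ranges.

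**1. The plan's own figure.** A two-sample t-test for 0.40 SD at 80% power needs 100 per arm; 100/0.75 = 133.3, so 134 per arm and 268 in total. Power at 100 per arm is 80.4%. This agrees with "A total of 200 participants for analysis will provide 80% power to detect a clinically meaningful difference of 0.40 standard deviation units". The calculation uses no covariates, so the sample size does not depend on this point. It also means that 0.40 is in units of the outcome SD.

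**2. How easily the imbalance trigger fires.** If it is read as p<0.05 on k independent variables, the chance of at least one flag is 1 − 0.95^k: 14% for k = 3 and 23% for k = 5. Read literally, as any imbalance at all, it would admit nearly every variable.

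**3. Type I error by reading of the rule.** Simulation: 268 randomised in stratified blocks of 4, 6 or 8; a random 200 analysed; three independent covariates plus the stratum (30% share, gap 0.3 residual SD); both triggers at p<0.05. Residual SD is the error SD after baseline Katz and all candidates. Significance is counted in either direction, so results favouring usual care are included.

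| Reading | Effect 0 | 0.15 | 0.25 |
|---|---|---|---|
| Mechanical: all triggered covariates enter | 4.9% | 4.9% | 5.0% |
| All candidates always in | 4.9% | 4.9% | 5.1% |
| Choice of two: baseline-only or all triggered | 5.8% | 5.8% | 6.4% |
| Smallest p over any triggered subset | 5.3% | 6.7% | 9.0% |

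The choice-of-two row comes from a separate run of 8,000 replicates (simulation error about 0.26 points), in which the any-subset figures were 5.9/6.6/8.6%. The other rows use 40,000 replicates. With candidates correlated at 0.3, choice of two gives 6.0/6.9/7.1% and any subset 6.1/8.3/10.5%. With five independent candidates, any subset gives 5.4/7.8/12.3%.

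**4. How often permitted models disagree on p<0.05.** At a true effect of 0.40 outcome SD and baseline–outcome correlation 0.6: 1.0/3.3/6.1% of trials over any triggered subset, and about 1.2/2.5/4.2% for the choice of two.

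**5. The missing threshold alone.** Under *will*, defining imbalance as p<0.05 or as a standardised difference above 0.10 selects different covariate sets in 81/56/24% of trials. The verdict changes in only 0.8/0.7/0.3%.

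**6. Leaving out the stratum.** With share s and gap d (in residual SD), the omitted factor inflates the model's error variance to 1 + s(1−s)d², while stratification keeps it largely out of the treatment comparison. The standard error is therefore overstated by about √(1 + s(1−s)d²):

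- s = 0.20, d = 0.3: √1.0144 = 1.007
- s = 0.40, d = 0.3: √1.0216 = 1.011
- s = 0.20, d = 0.5: √1.0400 = 1.020
- s = 0.40, d = 0.5: √1.0600 = 1.030

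Simulation gives 1.0065, 1.0101, 1.0193 and 1.0289, with type I error of 4.5–4.9%. Power falls by 0.2–0.8 points at correlation 0.6, and by 0.4–1.3 points at 0.4.

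**The case against.** Much of the plan is firm. Outcome, time point, treatment term, baseline Katz, estimator, alpha and sidedness are all fixed, and only the extra covariates are open. The protocol's *will* is already a rule without discretion, and under it type I error stays near 5%. The outcome-based trigger does no harm alone, because step 3 shows no inflation when it is applied mechanically. The SAP describes no search over subsets, so the natural reading of *may* is the choice of two. The documents also describe masking: "Outcome measures will be assessed by interviewers and analysts masked to treatment assignment and without interventionist contact". And the stratum could still enter as a clinical variable through either trigger.

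Most of this stands, and it sets the size of the point. Three things remain. The SAP says *may*, so the two statements conflict on the primary model. Masking reduces the scope for a motivated choice but does not remove it: judging imbalance needs at least coded groups, and a two-sided p-value is the same whichever arm carries which code. And a factor important enough to stratify on should not depend on a trigger to reach the primary model.

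A reader might infer that the plan has inflated type I error built in, or that the true rate is 9% or more. The documents do not support that: such figures need a deliberate search that the SAP does not describe, and covariate effects that the documents do not give. Nor should one infer that the stratum is barred from the model or that omitting it favours CAPABLE. It is unnamed, and omission errs on the conservative side.

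**Conclusion.** The point holds at moderate weight. The stratum that the trial randomises by is absent from both statements of the primary model, and the SAP permits more than one primary p-value where the success criterion needs one.

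The rule applied mechanically is sound on type I error, and the undefined imbalance threshold barely matters without discretion. With discretion, type I error is about 5–7% for the choice of two models. It is about 5–9% for a search over all triggered subsets, an upper bound for three independent covariates plus the stratum; more candidates or correlated ones would raise it. Omitting the stratum overstates the standard error by about 1–3%. All these sizes rest on assumed covariate effects of 0–0.25 residual SD, stratum gaps of 0.3–0.5 residual SD and shares of 20–40%. The textual findings need no assumption. The change is worth making because it replaces a data-driven rule with a better model at no cost, not because the design is invalid.

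**What to change.** In protocol E3 (aim 1) and in the SAP's Statistical Test of Hypothesis (Primary Outcome), state one identical primary model: 20-week Katz score on treatment, baseline Katz, the surgical/non-surgical stratum and a closed covariate list fixed before unmasking. The plan's own gender, Charlson index and pre-hospitalization ADL function would be an acceptable list. Move the imbalance and correlation triggers to sensitivity analyses.

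The cost is wording only. The three covariates are already collected at baseline (Table 1) and the stratum is known at randomisation. The baseline-only model has 200 − 3 = 197 residual degrees of freedom; four added terms leave 193. The 268 enrolled are unchanged. At 0.40 outcome SD and correlation 0.6, power is 93.9/95.1/96.8% for the fixed model against 94.0/94.7/96.6% for the mechanical rule (covariate effects 0/0.15/0.25), so nothing material is lost.
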